Official title: The acute effect of instant coffee in different forms on plasma metabolites

NCT number: XXX

Document date: May 23, 2025

Study Protocol and Statistical Analysis Plan

The procedures are as follows:

1. Do not consume coffee, tea, chocolate, or other caffeinated foods and drinks for the whole day (i.e. 24hrs) before the study.
2. Take informed consent that explains what is in the capsule, what is done with the data, and the risks of a blood draw.
3. Venous fasting blood draw in the morning.
4. Ingestion of the capsule or a cup of coffee beverage after the blood draw.
5. Answer a short questionnaire (age, sex, race, education level, alcohol use, usual coffee and tea use [green, Oolong, black tea], intake of fruit, vegetables, legumes, whole grains, menopausal status, oral contraceptive use [affects caffeine metabolism])
6. Another venous blood draw after 1 hour.
7. Process and store the blood correctly.

Recruitment of study participants

Study participants (n=15) will be recruited via flyers (e.g., shopping malls, MRT stations, neighbourhood shops, community centres, food centres, tertiary institutions such as NUS), advertisements at on-campus notice boards, bus-stops and newspapers. Recruitment email within NUS will be sent by the respective administrative officers of the project team members. Recruitment will also be conducted through online platforms such as Telegram, Facebook and Instagram, as well as snowballing and convenience sampling through referrals. Participants will be screened for their eligibility over a phone call with a screening questionnaire before they are enrolled into the study.

A short screening questionnaire will be administered to each participant to obtain information on their basic demographics, lifestyle, and medical history. Inclusion criteria include individuals aged 21-64 years old and of Chinese ethnicity. Exclusion criteria include pregnancy, specific medication use including recent use of antibiotics, presence or history of diseases (e.g., cancer, cardiometabolic, endocrine), major surgical operations, depression, anxiety, caffeine intolerance, fear of needles and/or blood disorders. Written informed consent will be obtained from each participant prior to the

commencement of the study.

Briefing session and informed consent

A briefing session will take place before the day of the study visit through an arranged Zoom/phone call. Participants who opted for a zoom call will be sent a scheduled meeting link, where he/she will be briefed by a study team member and/or PI/ Co-I. Over the call, researchers will explain the project aims and intervention study, and answer questions that the participants may have. Participants will be given or emailed handouts on foods/drinks not allowed to be consumed one day (i.e. 24hrs) before the visit (if the visit is scheduled at 8am, participants should abstain from the stated food/drinks from the day before at 8am). Participants will also be reminded to bring their medication and dietary supplements along to visit 1 for recording purposes.

Written informed consent will be obtained from each participant on the day of the first study visit. This will be performed by a study team member and should be completed within half an hour prior to the start of the study. Only participants who consent and completed the study visit(s) will be compensated. Participants will be reimbursed \$50 at the end of the second study visit. Participants who wish to withdraw after completing the first study visit will be reimbursed \$20.

Pre-study Commencement:

Before commencing the study visits, participants will be requested to fast overnight (8-12h). Drinking plain unflavoured water is allowed. Participants will be told to avoid vigorous physical activity except for activities of daily living for at least 24 hours prior to the session.

The day (24 hrs) before the study visits, participants will also be requested to avoid certain foods and beverages that may confound the study design including coffee and tea, coffee or tea-flavoured foods, caffeine-containing beverages (i.e., Coca-Cola, energy drinks), supplements containing caffeine or of herbal/botanical origin, chocolate, and chocolate-containing foods. We will communicate this over a phone call/messaging app with the participants before commencing the study, and provide a pamphlet

containing pictures and a detailed list of “allowed” and “non-allowed” foods and beverages.

Study Visit and Blood Collection:

The 2 study visits will take place at Investigational Medicine Unit (IMU), NUS Yong Loo Lin School of Medicine, with random assignment to either coffee capsules first or coffee as a beverage first. Each participant should go through both capsule and beverage interventions. The number of participants randomised to start with the capsule will be similar to those starting with the beverage. During each visit, 12 mL of venous blood will be collected at 2 time points each – at fasting and 1 hour after the consumption of the coffee capsule/drink. During the first visit, we will also ask the participant to fill out a questionnaire about their personal characteristics (DOB, gender, education level, smoking habits, height, weight, usual [referring to the past year] consumption of coffee and tea [number of cups per day of caffeinated and decaffeinated], soft drinks with caffeine such as cola, energy drinks such as Red Bull, chocolate, and key foods in the diet such as fruits and vegetables, alcohol use, dietary supplement use, medication use, menopausal status (Annex E). The period between 2 study visits will range between 7 to 28 days.

Ingestion of coffee capsule

A single dose will be provided to participants, in the form of two capsule or one cup of coffee beverage containing 1.7 grams a commonly used commercially available instant coffee (NESCAFE Taster's Choice House Blend Coffee Stick Packs consisting of 100% coffee beans and no other ingredients). 1.7 grams of instant coffee is the amount recommended for 1 cup of instant coffee by the manufacturer. Based on our previous measurements of caffeine in this coffee (Wedick, N.M., et al. Effects of caffeinated and decaffeinated coffee on biological risk factors for type 2 diabetes: a randomized controlled trial. Nutr J 2011;10, 93) the amount of caffeine for this amount of coffee is 59 mg which is substantially lower than the amount of coffee in a standard cup of brewed coffee which typically contains 92 mg of caffeine and much lower than the maximum amount of caffeine recommended per occasion which is 200 mg (EFSA Panel on Dietetic

Products, Nutrition and Allergies. Scientific Opinion on the safety of caffeine. EFSA J. 2015;13:4102.). The capsule used will be gelatin capsules that are purchased from NTUC FairPrice online. The brand is Now Foods. While the capsules are bovine sourced gelatin, it is not certified Halal or Kosher. The product empty capsules are produced under GMP (<https://www.nowfoods.com/now/about-now/seals-certifications/gmp>).

Sample processing and extraction

Blood will be collected in 4 Vacutainer® serum tubes (6mL each) and allowed to clot/stand at room temperature. After 30-40 min, serum will be separated from entire blood by centrifugation (2000g, 10 min, 24°C) and aliquoted into 1.5mL tubes. The remaining portion of samples that are left after serums have been separated from the samples will be discarded immediately after separation. All samples will be processed on the same day that they are collected. Samples will be stored at -80°C until all samples have been collected at the end of the intervention study and processed in a single batch. Briefly, thawed samples will be added with deuterated internal standards (for measure of control for extraction). Serum samples will be de-proteinised with acidified methanol, centrifuged (4000g, 10 min, 4°C) [15] and transferred into glass vials.

After collection of the blood samples at NUS, they will be transported to the NTU laboratory for measurements. Remaining samples may be stored NUS Saw Swee Hock School of Public Health Tissue Repository for up to 10 years for future measurements that are related to biomarkers of coffee intake and biomarkers related to its potential health effects, with the approval from the ethics board.

Targeted and untargeted metabolomic profiling

Serum samples will undergo targeted metabolomic profiling at the Singapore Phenome Centre located at NTU, which has state-of-the-art mass spectrometers and strong technical support. Targeted detection and quantification of a list of previously proposed coffee biomarkers (see metabolite assay list below) will be conducted on the serum samples using a Waters Acquity UHPLC-TQ-MS, and commercially available standards and deuterated standards. For atracyligenin, its lack of standard previously limited its detection but we have successfully synthesised this compound from its atracyloside

precursor, which can be used for level I identification and accurate quantification in this project. A quality control extract of pooled serum from all study participants will be injected at the beginning and end of each run, and in-between every 10 samples.

Data processing and Compound identification

Quantification of the biomarker compounds will be processed using MassLynx (Waters-specific software).

Metabolite assay

1. Atractyligenin
2. Trigonelline (HCl)
3. Caffeine
4. Theobromine
5. Theophylline (1,3-Dimethylxanthine)
6. Paraxanthine (1,7-Dimethylxanthine)
7. Caffeic acid
8. 3,4-dihydroxyhydrocinnamic acid (dihydrocaffeic acid)
9. Quercetin
10. Cyclo(Pro-val)
11. Cyclo(Leu-Pro)
12. 5-Acetylamino-6-formylamino-3-methyluracil
13. 5-Acetylamino-6-amino-3-methyluracil hydrate
14. 3-CQA (Chlorogenic acid)
15. 1-methylxanthine
16. Kaempferol
17. 1-methyluric acid

18,1,7-dimethyluric acid

Statistical analysis

We will calculate mean changes in serum concentrations of biomarkers between the fasting state and after ingestion of the capsule or coffee with corresponding 95% confidence intervals. Furthermore, we will test whether changes in concentrations differ between the coffee and the capsule intervention using paired t-tests.

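### The last meal and the length of the 8-12 h fast are not matched between the two visits, which adds small, avoidable noise for any analyte that also comes from food

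*Combined protocol and SAP*

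**What the plan says.** Under Pre-study Commencement, participants are asked to "avoid certain foods and beverages that may confound the study design including coffee and tea, coffee or tea-flavoured foods, caffeine-containing beverages", followed by "supplements containing caffeine or of herbal/botanical origin, chocolate, and chocolate-containing foods". The same section promises a pamphlet "containing pictures and a detailed list of" allowed and non-allowed items, and the briefing section mentions handouts. The contents of neither are in the document. Item 1 of the numbered procedures gives a shorter version of the rule, built on coffee, tea, chocolate and other sources of caffeine.

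On fasting, the text is "participants will be requested to fast overnight (8-12h", with plain water allowed. No standard or repeated last meal, no record of the previous day's diet and no recording of the actual fasting time is described.

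Diet is covered by questionnaire. Item 5 of the procedures lists "intake of fruit, vegetables, legumes, whole grains". Under Study Visit and Blood Collection the questionnaire belongs to the first visit and concerns "usual [referring to the past year] consumption of coffee and tea" together with key foods.

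At each visit blood is drawn "at fasting and 1 hour after the consumption of the coffee capsule/drink". The Metabolite assay list has 18 entries, among them quercetin, kaempferol, caffeic acid, dihydrocaffeic acid, 3-CQA and two cyclic dipeptides. The Statistical analysis section reports the mean change for each form with a 95% confidence interval and compares the two changes by paired t-test. No covariate is named, and no coffee-free visit is planned.

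**The concern.** The assay reaches beyond caffeine and its metabolites, while the foods named in the printed text are coffee, tea, sources of caffeine, chocolate and certain supplements. If some of the other analytes also come from ordinary foods, a participant may arrive at the fasting draw with residue from dinner. That residue keeps falling during the test hour, and the fall is counted in the change attributed to coffee.

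Two consequences need to be kept apart. The mean change within each form has no control, so a fall shared by all participants pulls it downward. The capsule-minus-beverage difference is affected only through the difference in residue between a participant's two visits. With a different dinner and a fast of 8 h at one visit and 12 h at the other, that difference adds variance to a comparison resting on 15 people. A questionnaire on usual intake cannot describe the meal eaten before either visit.

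**Working it through.** **Nothing to reproduce.** The plan gives n=15 without a significance level, power, effect size or SD, and it gives no half-lives or meal-related concentrations. Everything below except the fasting window, the 1 h interval and n=15 is an assumption.

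**Step 1: size of the drift.** Assume first-order decay with half-life *h* from a post-meal level of 1, starting when the fast starts. After a fast of *T* hours:

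- residue at the fasting draw = 2^(-T/h)
- fraction of that residue lost in the next hour = 1 - 2^(-1/h)
- drift in the 1 h change = 2^(-T/h) × (1 - 2^(-1/h))

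For the same dinner, drifts after two fasts that differ by *k* hours stand in the ratio 2^(k/h).

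| Assumed h | 1 h fall in residue | Drift, 8 h fast | Drift, 12 h fast | Drift ratio, 4 h apart | Drift ratio, 1 h apart |
|---|---|---|---|---|---|
| 1 h | 50.0% | 0.20% | 0.01% | 16 | 2.0 |
| 2 h | 29.3% | 1.83% | 0.46% | 4.0 | 1.41 |
| 3.5 h | 18.0% | 3.68% | 1.67% | 2.2 | 1.22 |
| 6 h | 10.9% | 4.33% | 2.73% | 1.6 | 1.12 |
| 11 h | 6.1% | 3.69% | 2.87% | 1.3 | 1.07 |
| 28 h | 2.4% | 2.01% | 1.82% | 1.1 | 1.03 |

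The drift columns are shares of the post-meal level.

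**Step 2: the ceiling.** Put x = 2^(-1/h). The drift is x^T (1 - x), which is largest at x = T/(T+1).

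- T = 8: (8/9)^8 × 1/9 = 0.0433, at h of about 5.9 h.
- T = 12: (12/13)^12 × 1/13 = 0.0294, at h of about 8.7 h.

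So whatever the half-life, the drift is at most 4.3% (8 h fast) or 2.9% (12 h fast) of the post-meal level. A level that peaks some time after the meal shortens the effective decay time and would raise these ceilings somewhat.

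**Step 3: bias or noise.** Both visits were simulated with fasts uniform on 8-12 h and dinners drawn independently at each visit (lognormal, log-SD 0.5, assumed). Results are shares of the median post-meal level.

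| Assumed h | Mean within-form drift | Mean between-form drift | SD of between-form drift per participant |
|---|---|---|---|
| 3.5 h | -2.9% | about 0 | 2.4% |
| 11 h | -3.7% | about 0 | 2.8% |
| 24 h | -2.4% | about 0 | 1.8% |

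**Step 4: cost in power.** For a paired t-test with n=15 and two-sided 0.05 (assumed), the noncentral t gives 80% power at a standardised difference of 0.778. If the drift SD is *r* times the between-form SD without drift, the SD grows by √(1 + r²):

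- r = 0.10: SD × 1.005, power 79.6%
- r = 0.25: SD × 1.031, power 77.6%
- r = 0.50: SD × 1.118, power 70.8%

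The documents do not show which *r* applies to any analyte.

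**The case against.** The strongest reply is that this is a small matter, and much of that reply stands.

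- **The avoid list.** A reader might infer that the restriction covers caffeine sources and little else. The document does not show this. The list is introduced as a set of examples, the pamphlet's contents are not available, and the herbal or botanical supplements are barred without any caffeine condition. It can only be said that the printed text names no other food source.
- **Food origin.** Nothing in the document says that the listed compounds come from allowed foods; it calls the panel previously proposed coffee biomarkers. The questions on fruit, vegetables, legumes and whole grains hint that such foods were thought relevant, but do not establish it. The premise remains an assumption.
- **Size.** Figures such as a 29% fall in one hour, or a fourfold difference in drift between an 8 h and a 12 h fast, look alarming. Both belong to a 2 h half-life, where only 6.25% (8 h) or 1.6% (12 h) of the post-meal level is left. The drifts themselves are then 1.8% and 0.5%. The 8 h against 12 h contrast is also the extreme of the window, not a typical pair of visits.
- **Adjustment.** A reader might infer that nothing collected on the day could correct for the drift. That is not so. Under the model the drift is a fixed fraction of the meal residue, and the fasting sample at each visit contains that residue. Baseline adjustment is possible from data already planned, though imperfect if other sources contribute to the fasting level. The plan does not specify it.

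The objection does not remove the point that the meal and fasting length are left free to differ between a participant's visits, and that matching them costs little.

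**Conclusion.** The point holds as a cheap improvement of optional priority. The printed plan allows an 8-12 h fast and does not ask for the same last meal or fasting length before both visits. For an analyte that also comes from food, part of the 1 h change may be decay of that meal: at most about 4.3% of the post-meal level after 8 h and 2.9% after 12 h. This matters only where coffee adds little by 1 h.

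It would be tempting to conclude that the capsule-versus-beverage result is biased. The documents do not support that: order is randomised, so the drift averages to about zero in the paired difference and only adds variance. The loss of power is trivial at a drift SD of 0.10 of the between-form SD and reaches about 9 percentage points (80% to 70.8%) at 0.50, a ratio for which the documents give no support. The within-form mean changes have no such protection and may be slightly too low.

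These sizes rest on first-order decay, assumed half-lives, assumed meal variation, a two-sided 0.05 test and the unstated premise of other food sources.

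**What to change.** In Pre-study Commencement and the existing pamphlet:

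1. Ask participants to note the evening meal before visit 1 and the time they finished it.
2. Ask them to repeat that meal before visit 2, with a fasting length within about 1 h of the first and inside the 8-12 h window.
3. Record the actual fasting time at both visits.

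For the same dinner and a 2 h half-life, holding the fasts within 1 h limits the ratio of the two drifts to 1.41, against 4.0 across the full window; at longer half-lives both ratios are closer to 1.

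Repeating the meal equalises the drift between visits but does not remove it, so the slight downward bias in the within-form means remains. Changes within each form should therefore be read with caution for analytes not specific to coffee. Extending the list of foods to avoid is not part of this recommendation, because it would rest wholly on the unverified premise about food sources.

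The cost is a few lines in the pamphlet and reminder message, one recorded time per visit and a small added burden on participants. No extra samples, visits or staff are needed.

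### Does the plan need to say whether the hour before the second blood draw runs from the start or the end of intake?

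*Combined protocol and SAP*

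**What the plan says.** The section Study Visit and Blood Collection sets two draws per visit, "at fasting and 1 hour after the consumption of the coffee capsule/drink". The numbered procedure list at the start of the document puts intake at step 4, "Ingestion of the capsule or a cup of coffee beverage after the blood draw". A questionnaire follows at step 5, and step 6 is "Another venous blood draw after 1 hour".

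Under Ingestion of coffee capsule, the dose is given "in the form of two capsule or one cup of coffee beverage containing 1.7 grams" of instant coffee. The Statistical analysis section will "test whether changes in concentrations differ between the coffee and the capsule intervention using paired t-tests". It describes the change as running from the fasting state to after ingestion.

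The documents state no drinking time, no limit on it and no window around the draw. They do not ask for the clock times of intake and draw. The visit worksheets are not part of what can be read here, so whether those times are recorded is unknown.

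**The concern.** Each form has a single post-dose sample, so no concentration curve is available to absorb a shift in timing. Two capsules are gone in moments, while a cup takes minutes. Moving the anchor from the end to the start of intake therefore moves the cup draw earlier by the whole drinking time and hardly moves the capsule draw. The shift attaches to the beverage at every visit, so neither the randomised order nor the pairing cancels it. The only comparative test has no term for elapsed time.

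At stake would be a difference between forms that reflects when blood was drawn rather than how the coffee was absorbed, with a direction that depends on an anchor the text does not spell out. Timing both forms from the midpoint of intake looks like a cheap remedy.

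**Working it through.** **1. What the text says.** Three places bear on the anchor, and all point the same way.

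| Place | Wording in substance | Natural anchor |
|---|---|---|
| Study Visit and Blood Collection | one hour after consumption of capsule or drink | intake finished |
| Procedure list, steps 4 to 6 | ingest, questionnaire, then draw after an hour | intake finished |
| Statistical analysis | change from fasting to after ingestion | intake finished |

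Nothing suggests timing from the first sip.

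**2. The offset under that reading.** If a cup is drunk evenly over D minutes, the mean age of the dose at the draw is 60 + D/2 min when timed from the end and 60 − D/2 min when timed from the start. Capsules are at about 60 min.

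| D (assumed) | From start | From end |
|---|---|---|
| 5 min | 57.5 | 62.5 |
| 10 min | 55.0 | 65.0 |
| 15 min | 52.5 | 67.5 |

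**3. What that does to the concentration.** All inputs here are assumptions: one compartment, identical absorption from both forms, absorption rate ka of 1, 2 or 4 per hour, and half-life of 5, 1 or 0.5 h.

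- C(t) = ka/(ka − ke) × (exp(−ke·t) − exp(−ka·t)), with ke = ln 2 / half-life and t in hours.
- With d = D/60, E is the mean of C over 1 to 1 + d (end anchor), and S is the mean over 1 − d to 1 (start anchor).
- The offset against capsules is E/C(1) − 1 or S/C(1) − 1.

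Two examples at D = 10:

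- ka = 1, half-life 5 h: C(1) = 0.5836 and E = 0.6057, an offset of +3.8%.
- ka = 4, half-life 0.5 h: C(1) = 0.3546 and E = 0.3212, an offset of −9.4%.

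All nine end-anchored offsets at D = 10:

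| | half-life 5 h | 1 h | 0.5 h |
|---|---|---|---|
| ka = 1 | +3.8% | +0.9% | −1.9% |
| ka = 2 | +1.4% | −2.1% | −5.7% |
| ka = 4 | −0.6% | −4.7% | −9.4% |

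The median size is 2.1%. Over D = 5, 10 and 15 (27 cases) the range is −13.8% to +5.5%.

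**4. Effect on the t-test.** With n = 15 and df = 14, the noncentrality is offset / (SD/√15). For the median offset and an SD of 20% of the capsule rise, it is 2.07 / (20/3.873) = 0.40, and the nominal 5% test rejects 6.6% of the time. The nine cases run from 5.1% to 39.7%. With an SD of 40%, the median is 5.4% and the range 5.0% to 13.6%. These count as false positives only if drinking time is held not to be part of the effect of form.

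**5. What the midpoint would gain.** With even drinking, the midpoint anchor leaves −0.25% to +0.21% over the 27 cases. That depends on even or symmetric drinking. If the cup is drunk faster at first (triangular, mean intake at D/3), the midpoint is off by D/2 − D/3 = D/6. The residual is then −4.7% to +1.9%, and the midpoint does worse than the start anchor in 2 of the 27 cases.

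**The case for a change.** The strongest case for a change is that the wording is not explicit, the offset is systematic, and a few words and 90 clock times (15 participants × 2 visits × 3) would settle it. Times not noted at the visit cannot be reliably recovered. The assay list has 18 compounds that need not share one kinetic profile, and rapidly cleared ones could be shifted by more than a few percent. If the hour did run from the start of intake, the cup result would differ from the end-anchored one by a factor E/S: −17.8% to +8.6% at 10 min and −25.3% to +13.3% at 15 min.

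Part of this stands. The text could be more explicit, and the offset at the end of intake is real. Front-loaded drinking widens that offset from D/2 to 2D/3, so the midpoint would still be closer than the end anchor.

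The rest does not carry. The E/S figures set the ordinary reading against one the text never suggests, so they do not measure a live ambiguity. The argument that the two anchors give opposite signs holds on the 27-case grid, but on a finer grid the signs agree in 869 of 14,820 cases (about 6%), where the peak lies near one hour. The 39.7% rejection rate is one corner: the fastest absorption, the shortest half-life and the smaller of the two assumed SDs. The model also covers only directly absorbed compounds, not those formed in the body from caffeine. Finally, a short protocol's silence on clock times is weak evidence that the worksheets omit them.

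**Conclusion.** No change to the plan is needed. Read in the ordinary way, the second draw comes one hour after intake is finished, under one rule for both forms. The paired t-test then estimates a sound contrast, namely the difference in serum change one hour after finishing a cup or two capsules. Leaving the anchor, window and clock times unspelled is missing operational detail that staff can be expected to fill sensibly.

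Moving to the midpoint answers a different question: forms compared at equal time since mean intake. The trial compares coffee in different forms, and slower intake is part of drinking a cup, so counting it in the effect is legitimate. The midpoint would narrow the offset, but would nearly remove it only if cups are drunk evenly or symmetrically.

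The size of the residual offset rests wholly on assumed drinking times, kinetics and SDs. On those assumptions it is typically about 2% for a 10-minute cup, and reaches 13.8% in the most extreme of the 27 cases (a 15-minute cup, fast absorption, half-life of half an hour). Two things would change this view: evidence that site staff start the clock at the first sip for some visits and the last for others, or drinking times well beyond 15 minutes.

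### With 15 people and possibly skewed metabolite responses, does the plan need skew-robust intervals, a below-limit rule and a ratio analysis?

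*Combined protocol and SAP*

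**What the plan says.** The Statistical analysis section is two sentences long. One promises "mean changes in serum concentrations of biomarkers between the fasting state and after ingestion of the capsule or coffee with corresponding 95% confidence intervals". The other adds that "we will test whether changes in concentrations differ between the coffee and the capsule intervention using paired t-tests".

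The rest comes from elsewhere in the document:

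- **Size and design.** "Study participants (n=15) will be recruited via flyers" (Recruitment of study participants) and "Each participant should go through both capsule and beverage interventions" (Study Visit and Blood Collection). Each within-form mean therefore rests on at most 15 changes, and so does the paired comparison.
- **Time points.** Blood is taken "at fasting and 1 hour after the consumption of the coffee capsule/drink", at both visits.
- **Abstinence.** For the day before each visit, "participants will also be requested to avoid certain foods and beverages that may confound the study design including coffee and tea" (Pre-study Commencement).
- **Assay.** The metabolite list has 18 entries. The sections on profiling and data processing cover standards, quality-control injections and software. They state no quantification limit and no rule for results below it.

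No interval method is named. Because the only named test is the paired t-test, t intervals are the natural reading.

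**The concern.** Blood levels of dietary metabolites may well be right-skewed, and 15 is a small number for relying on the central limit theorem. A t interval for the mean of a skewed variable covers less than its nominal level, and it misses mostly by lying too low. The within-form mean changes are the first output that the plan names, so intervals that claim 95% and deliver less would weaken a main result.

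Two further gaps seem to add to this. Fasting samples follow a day without coffee, tea or chocolate, so some may fall below the quantification limit. Every change subtracts a fasting value, so an unstated rule could move the mean or decide who enters the paired comparison. And where fasting levels are near zero, a few high responders could inflate the variance of the raw difference and hide a form effect that a ratio would show.

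**Working it through.** **1. The plan's own figure.** The documents give one figure to reproduce, the 95% level. With n=15 the t interval is mean ± t(0.975, 14 df) × SD/√15 = mean ± 2.145 × SD/3.873 = mean ± 0.554 SD. With normal changes (200,000 simulated samples) it covers 95.0%, with 2.5% of misses on each side. The stated level is met under normality.

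**2. Under assumed skew.** The documents give no distributional data, so the log-SD is an assumption shown over a range. Changes are lognormal and n=15. The t column uses 200,000 samples; the bootstrap-t column uses 3,000 samples with 999 resamples each.

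| log-SD | skewness | t interval | bootstrap-t |
|---|---|---|---|
| 0.25 | 0.8 | 94.5% | not run |
| 0.5 | 1.8 | 92.5% | 94.7% |
| 0.75 | 3.3 | 89.7% | 92.9% |
| 1.0 | 6.2 | 85.6% | 91.5% |
| 1.25 | 13 | 80.4% | 88.8% |

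Gamma changes with skewness 1, 2 and 2.8 give t-interval coverage of 94.0%, 91.1% and 87.9%. If the change is a lognormal fasting level with about a threefold rise, coverage runs from 91.4% down to 78.1%.

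**3. What a miss does.** At log-SD 0.75 the interval lies wholly below the true mean in 10.0% of samples and wholly above it in 0.3%. The error is understatement. The interval still excludes zero in 99.6% of samples at log-SD 0.8 and 97.1% at 1.0. When it misses low, its upper limit falls short of the true mean by a median of 5%, 9% and 12% at log-SD 0.5, 0.8 and 1.0.

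**4. The replacement interval.** Bootstrap-t covers 94.7% with normal changes, so it loses little there. Under lognormal skew it is 2% to 27% wider (median) and still short of 95%. With symmetric heavy-tailed changes it covers 92.7% against 95.8% for the t interval. When only a few people respond, its median width is 2.4 times that of the t interval. Johnson's skewness-adjusted t gains no more than about 1 point.

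**5. The between-form test.** With equal means and equal spread (log-SD 0.5 to 1.25, correlation 0 to 0.8), the paired t-test rejects in 2.6% to 4.6% of trials, which is conservative. With equal means and unequal spread (for example log-SD 0.5 against 1.0) it rejects in 5.2% to 11.7%. A different interval for the within-form means does not touch this test. A test on logs asks another question: with equal arithmetic means and log-SDs of 0.5 and 1.0, the geometric means differ by exp[(1.0² − 0.5²)/2] = exp(0.375) = 1.45-fold.

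**6. Below-limit results.** Assume a fasting log-SD of 0.75, a true twofold rise and a true mean change of 1.545. Mean change by substituted value:

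| fasting values below limit | zero | half the limit | the limit |
|---|---|---|---|
| 30% | 1.63 | 1.57 | 1.50 |
| 60% | 1.74 | 1.55 | 1.35 |
| 90% | 1.63 | 1.27 | 0.91 |

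The choice matters when censoring is heavy, and no single convention is right throughout. For the form comparison, a common substitute s cancels in anyone whose fasting value is below the limit at both visits: (beverage − s) − (capsule − s) = beverage − capsule.

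**7. The ratio analysis.** Assume a 1.25-fold form effect, within-person log-SD 0.2 and fasting near zero. Power for the raw test against the log ratio of increments is 74% against 78% at log-SD 0.3, 69% against 79% at 0.5, and 56% against 79% at 0.8. None of these inputs is in the documents.

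**The case for a change.** The strongest case for a change is that it is cheap and should be made before the data are seen. A few lines would fix the interval method and the below-limit rule. With 15 people, a normality check after the fact has little power and invites a separate choice for each of 18 analytes. The below-limit gap does not depend on skew at all. If below-limit results were simply left missing, three per visit would leave between 15 − 6 = 9 and 15 − 3 = 12 complete pairs, and power for the assumed effect at log-SD 0.3 would fall from 74% to between 48% and 63%.

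Much of this stands. The coverage arithmetic is sound, the rule is absent, and a reader of the results will want to know how many values were below the limit.

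It does not carry the conclusion. The loss runs from half a point to ten points or more, and nothing in the documents says where any analyte falls. Bootstrap-t exchanges one set of failures for another at this sample size, so choosing it is a judgement on which statisticians can differ. The power loss needs an analyst to discard below-limit values, which the plan does not say. The usual handling is one substitution rule for all samples, with the share below the limit reported, and that keeps all 15 people in the analysis.

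**Conclusion.** No change is called for. If changes are right-skewed, t intervals for the within-form means under-cover at n=15: about 94.5% for mild skew and 85% to 86% at log-SD 1.0, mostly by lying too low. This rests on an assumed distribution and on reading the unnamed method as a t interval, so the plan is not shown to be wrong as written.

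Each of the three parts ends differently:

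- **Interval method: a fair trade-off.** The t interval is simple and exact under normality. Bootstrap-t improves coverage under skew, does not restore 95% when skew is strong, and behaves worse with heavy tails or few responders.
- **Below-limit rule: a gap that analysts fill sensibly.** One rule for both forms, with the share affected reported per analyte, is ordinary practice once the assay limits are known.
- **Ratio of increments: no gain for the planned results.** It is an optional extra that answers a different question from the mean difference in change.

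The paired between-form test should not be taken as immune to skew. It holds its 5% level when the two forms have similar spread, and can reach about 5% to 12% when means are equal and spreads differ. That is a caution for interpreting a single small p-value, and none of the three measures would alter that test.
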